11.2 Adverse events

Adverse events with a start date prior to the first dose of IMP will be defined as pre-treatment AEs. A treatment-emergent AE (TEAE) is defined as any AE with a start date/time at the time of or after the first dose of IMP up until 140 days after the last dose of IMP. Any AE with onset later than 140 days after the last dose of IMP will not be considered as treatment-emergent and therefore will not be included in the tabulations of TEAEs. Where dates are missing or partially missing, AEs will be assumed to be treatment-emergent, unless there is clear evidence to suggest that the AE started prior to the first dose of IMP or later than the defined cutoff for TEAEs.

Handling of missing dates/times for classification of AEs as TEAEs is described in [Section 4.2.4](#).

All AEs will be recorded in the eCRF from informed consent until study completion or termination. All AEs will be coded and categorized by intensity (mild/moderate/severe) and relationship to IMP (related/not related).

An overview of the number and percentage of subjects who experience TEAEs will be presented by treatment group, based on the SS. This tabulation will include the number and percentage of subjects with any TEAEs, serious TEAEs, related TEAEs, discontinuation due to TEAEs, severe TEAEs, AEs leading to death and TEAEs leading to death; event counts will also be included.

In addition, the following summaries will be presented by treatment group, SOC, high level term (HLT) and PT, based on the SS:

- Incidence of TEAEs
- Incidence of TEAEs, stratified by overall anti-BKZ antibody status (positive/negative) as defined in [Section 10](#)
- Incidence of serious TEAEs
- Incidence of non-serious TEAEs
- Incidence of TEAEs by relationship
- Incidence of TEAEs by maximum relationship
- Incidence of TEAEs by maximum intensity
- Incidence of fatal TEAEs by relationship
- Incidence of non-serious TEAEs by relationship
- Incidence of serious TEAEs by relationship
- Incidence of non-serious TEAEs above threshold of 5% of subjects
- Incidence of non-serious TEAEs above threshold of 5% of subjects by relationship
- Incidence of TEAEs by SOC and PT (including the number and percentage of subjects and individual subject numbers for each PT stratified by intensity, relationship and seriousness)

In addition, separate summaries by treatment group, SOC, HLT and PT will be included for the following AEs for special monitoring (AESM):

- Major cardiovascular events
- Serious infections, opportunistic infections, fungal infections and tuberculosis (TB)
- Malignancies including lymphoma
- Cytopenias
- Neuropsychiatric events
- Inflammatory bowel disease
- Anaphylactic reaction (hypersensitivity and anaphylactic reactions)

- Hepatic events and drug induced liver injury

The criteria for identifying and additional criteria for reporting AESM are provided in [Section 14.9](#).

All summary tables (including those for AESM) will contain the number and percentage of subjects and the number of events where applicable. A subject who has multiple events in the same SOC, HLT and PT will be counted only once in the subjects counts but all events will be included.

In summaries including relationship to IMP, the following relationship categories will be included:

- Related
- Not related

Subjects who experience the same event multiple times will be included in the most related category for tabulations by maximum relationship. Events with missing relationship will be considered as 'Related' for summary purposes but shown as missing in the data listings.

In summaries including intensity, the following categories will be summarized:

- Mild
- Moderate
- Severe

Subjects who experience the same event multiple times will be included in the most severe category for tabulations by maximum intensity. Events with missing intensity will be considered as severe for summary purposes. All data will be presented as recorded in the database for the listings.

Adverse event summaries will be ordered by alphabetical SOC, alphabetical HLT within SOC and decreasing frequency of PT in the 'BKZ' column for tables including event counts. For tables including only number and percentage of subjects, summaries will be ordered by alphabetical SOC, alphabetical HLT within SOC and decreasing incidence of PT within HLT and SOC in the 'BKZ' column.

Listings will be presented by treatment group and subject for all AEs, SAEs, AEs leading to death and AEs leading to withdrawal. Listings will include the onset date/time and outcome date/time of the event (including relative days), the AE duration (derived), days since first dose of IMP, days since most recent dose of IMP, pattern of event, intensity, relationship, action taken and outcome. In addition, the listing will flag AEs that led to discontinuation, TEAEs, AESM and SAEs. All AE listings will be based on the ES, except where otherwise noted.

A glossary of all TEAE terms will be provided including the SOC, HLT, PT and reported term, based on the SS.

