5.1.2 Study duration per subject

For each subject, the study will last a maximum of 34 weeks. This includes the following study period durations:

- Screening Period: ≥ 2 weeks up to a maximum of 4 weeks, from the time of informed consent up to randomization and administration of IMP at Baseline (Visit 2).
- Treatment Period: Up to 12 weeks, from the administration of IMP at Baseline (Visit 2) to the assessment of the primary efficacy variable at Week 12 (Visit 11).
- SFU Period: Up to 20 weeks, from the last dose of IMP at Week 10 (Visit 10) to the SFU Visit at Week 30 (Visit 12).

The end of the study is defined as the date of the last visit of the last subject in the study.

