5.2 Schedule of study assessments

A schedule of study assessments is provided in [Table 5–1](#).

PUBLIC COPY
This document cannot be used to support any marketing authorization application and any extensions or variations thereof.

Table 5–1: Schedule of study assessments

Procedures	Screening Period	Treatment Period										SFU Period
	Visit 1	Visit 2	Visit 3	Visit 4	Visit 5	Visit 6	Visit 7	Visit 8	Visit 9	Visit 10	Visit 11	Visit 12/ SFU Visit/EW Visit
	Scr. ^a	Baseline Day 1 ^b	Week 2 (± 3 days) ^c	Week 4 (± 3 days) ^c	Week 5 (± 3 days) ^c	Week 6 (± 3 days) ^c	Week 7 (± 3 days) ^c	Week 8 (± 3 days) ^c	Week 9 (± 3 days) ^c	Week 10 (± 3 days) ^c	Week 12 (± 3 days) ^c	Week 30 (-3 to +7 days) ^c
Written informed consent	X											
Demographics and Baseline characteristics ^d	X											
Inclusion/exclusion criteria verification	X	X										
Significant past medical history and concomitant diseases	X	X ^e										
Hidradenitis suppurativa history	X											
Concomitant medications	X	X	X	X	X	X	X	X	X	X	X	X
Physical examination ^f	X	X	X	X		X		X		X	X	X
Body weight	X	X									X	X
Vital signs ^g	X	X	X	X	X	X	X	X	X	X	X	X
12-lead ECG	X	X		X				X			X	X
Pregnancy test ^h	X	X		X				X			X	X
Urine drug screen	X											
Hematology, biochemistry, urinalysis	X	X		X				X			X	X

Table 5–1: Schedule of study assessments

Procedures	Screening Period	Treatment Period										SFU Period
	Visit 1	Visit 2	Visit 3	Visit 4	Visit 5	Visit 6	Visit 7	Visit 8	Visit 9	Visit 10	Visit 11	Visit 12/ SFU Visit/EW Visit
	Scr. ^a	Baseline Day 1 ^b	Week 2 (±3 days) ^c	Week 4 (±3 days) ^c	Week 5 (±3 days) ^c	Week 6 (±3 days) ^c	Week 7 (±3 days) ^c	Week 8 (±3 days) ^c	Week 9 (±3 days) ^c	Week 10 (±3 days) ^c	Week 12 (±3 days) ^c	Week 30 (-3 to +7 days) ^c
Serology (HIV, Hepatitis B and C virus) ⁱ	X											
Chest x-ray or CAT scan of chest ^j	X											
TB questionnaire	X	X									X	X
IGRA TB test ^k	X											X
Blood sampling for plasma PK levels of bimekizumab ^l		X	X	X				X			X	X
Blood samples for PD and nonhereditary pharmacogenomic variables ^m		X						X			X	
Blood samples for pharmacogenetic variables ⁿ		X									X	
Blood samples for plasma levels of bimekizumab ADA ^o		X	X	X				X			X	X
Urine samples for biomarker research		X									X	

Table 5–1: Schedule of study assessments

Procedures	Screening Period	Treatment Period										SFU Period
	Visit 1	Visit 2	Visit 3	Visit 4	Visit 5	Visit 6	Visit 7	Visit 8	Visit 9	Visit 10	Visit 11	Visit 12/ SFU Visit/EW Visit

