10 IMMUNOLOGICAL ANALYSES

All immunological analyses will be performed for the PK-PPS. In this study, this will comprise an analysis of anti-BKZ antibody data only which will be listed and summarized at each scheduled visit, and the rate of anti-BKZ antibody positive subjects will be calculated.

The results of the anti-BKZ antibody analysis will be listed by treatment group and visit based on the SS. This will include the screening assay, confirmatory assay, titre (if applicable) and confirmation of whether or not the sample contains BKZ concentration levels above the drug tolerance.

A cut point will be determined by the bioanalytical laboratory that will be used to determine the status of anti-BKZ antibody as above the cut point (ACP) or below the cut point (BCP). For any anti-BKZ antibody levels that are ACP, a further confirmatory assay will be performed, the results of which will be determined as either 'confirmed positive' (CP) or 'not confirmed

positive' (NCP). For samples that are CP, a further titre assay will be performed and the anti-BKZ antibody titre will be reported.

The following definitions will be applied:

- An anti-BKZ antibody status of positive will be concluded for any subject with an anti-BKZ antibody level that is ACP and CP at any time point
- An anti-BKZ antibody status of negative will be concluded for any subject with an anti-BKZ antibody level that is either BCP or ACP and NCP at any time point
- A subject will be classified as having anti-BKZ antibody positivity at Baseline if the Day 1, predose result is ACP and CP
- A subject will be classified as having treatment-induced anti-BKZ antibody positivity when meeting 1 of the following criteria:
 - The Baseline result is either BCP or ACP and NCP, and at least 1 post-Baseline time point is ACP and CP
 - The Baseline result is positive (ACP and CP) and at least 1 post-Baseline measurement shows a pre-defined fold increase in titre from the Baseline value (the fold increase from Baseline required to meet these criteria will be defined with the development of the assay and will be included in the TFLs)
- A subject will be classified as overall positive if at least 1 post-Baseline measurement is ACP and CP (this includes subject who have negative results at Baseline)
- A subject will be classified as overall negative if at all post-Baseline visits the anti-BKZ antibody status is negative (this includes subjects who have positive [ACP and CP] results at Baseline)

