The number and percentage of subjects with a positive and negative anti-BKZ antibody status will be summarized at each visit and overall. This summary will exclude any samples with BKZ concentrations confirmed to be above the drug tolerance.

In addition, the first occurrence of treatment-induced anti-BKZ antibody positivity (based on the definitions above) will be summarized at each post-Baseline visit. This tabulation will present the number and percentage of subjects at each post-Baseline visit who fulfill at least 1 of the above defined criteria for treatment-induced positivity; subjects will be counted in the numerator based on the earliest visit at which 1 of these criteria is fulfilled. At other visits, subjects will be counted in the denominator (assuming a measurement is available). This summary will exclude any samples with BKZ concentrations confirmed to be above the drug tolerance.

For all tabulations, percentages will be calculated based on the number of subjects with non-missing data and anti-BKZ antibody levels that are not flagged as containing BKZ concentration levels above the drug tolerance at each respective visit.

A separate listing will be presented showing the BKZ concentrations and anti-BKZ antibody measurements in the same output in adjacent columns, based on the PK-PPS. The listing will include the BKZ concentration, anti-BKZ antibody status (ACP or BCP) and confirmatory assay results if applicable (NCP or CP), together with the titre for results that are CP. In addition, the time since the previous administration of IMP will be reported (in days).

Finally, individual subject plots will be presented displaying the anti-BKZ antibody titre and BKZ concentrations overlaid on the same figure. The figure will also show the timing and dose of each administration of BKZ received during the study. The anti-BKZ antibody data will be plotted using a semi-logarithmic scale. This figure will exclude any samples with BKZ concentrations confirmed to be above the drug tolerance.

The rules for handling values that are BLQ in the BKZ concentration data are described in [Section 4.2.2](#). For the anti-BKZ antibody data, any negative results for which there are no titres available at a specific visit will be substituted with 0.001 for the purpose of the figure.

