11.1 Extent of exposure

All IMP administration details (including date, time and location of injection) will be listed.

The percentage of injections administered will be included in the listing based on the number of planned injections. For subjects completing the study this will be 17 injections. The number of planned injections for subjects who withdraw early from the study will be reduced according to the number of injections planned up to EW visit.

All IMP administration details (including date, time and location of injection) will be listed. The percentage of injections administered will be included in the listing based on the number of planned injections. For subjects completing the study this will be 17 injections. The number of planned injections for subjects who withdraw early from the study will be reduced according to the number of injections planned up to EW visit.

The duration of exposure to BKZ and PBO (days) will be calculated as follows:

$$\text{Exposure} = (\text{Date of Last Dose} - \text{Date of First Dose}) + 140 \text{ days}$$

The duration of exposure to ADA (days) will be calculated as follows:

$$\text{Exposure} = (\text{Date of Last Dose} - \text{Date of First Dose}) + 100 \text{ days}$$

The number of days added to the BKZ and ADA exposure calculations are 5 times the half-life of each drug, respectively: 5 x 28 days for BKZ and 5 x 20 days for ADA. The number of days added to PBO is set to 140 days in order for PBO exposure to be comparable to that of BKZ.

Missed doses will not be accounted for in the calculation above.

Duration of exposure will be listed for each subject and summarized using descriptive statistics.

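### The TEAE table by overall anti-bimekizumab antibody status counts events that began before a subject's first positive sample as events in positive subjects, and no planned output shows the order

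*SAP*

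**What the plan says.** Among the adverse event summaries for the Safety Set, SAP 11.2 lists "Incidence of TEAEs, stratified by overall anti-BKZ antibody status (positive/negative) as defined in" SAP 10. The label comes from two rules there: "A subject will be classified as overall positive if at least 1 post-Baseline measurement is ACP and CP", and "A subject will be classified as overall negative if at all post-Baseline visits the anti-BKZ antibody status is negative". Neither rule refers to the onset of any adverse event. The positive rule is also not restricted to treatment-induced positivity, so a subject positive at Baseline and again afterwards is overall positive.

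Protocol Table 5-1, in the row "Blood samples for plasma levels of bimekizumab ADA", schedules samples at Baseline and at Weeks 2, 4, 8, 12 and 30. SAP 11.2 counts an event as treatment-emergent from the "first dose of IMP up until 140 days after the last dose of IMP". Protocol 5.1.2 puts the last dose at Week 10 and the Safety Follow-Up Visit at Week 30.

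One planned antibody summary does respect time. In SAP 10, "the first occurrence of treatment-induced anti-BKZ antibody positivity (based on the definitions above) will be summarized at each post-Baseline visit". It is not joined to adverse events. The AE listings in SAP 11.2 give days since the first and the most recent dose, but not days relative to the first positive sample.

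**The concern.** The stratum label is fixed by information that may arrive after the events it is used to sort. A subject who reports several events during dosing and first tests positive at the last visit contributes all of them to the positive stratum, although none followed a positive result. Compared with the negative stratum, the table could then show a difference that does not reflect events after antibodies appeared, or could dilute one that does.

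Observation time adds to this. The rule for overall negative sets no minimum number of samples, and the AE summaries give subjects, percentages and event counts without subject-time. A subject followed for longer has more chance both to test positive and to report an event.

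Safety and immunogenicity both belong to the secondary objective, and this is the only planned output that tabulates adverse events by antibody status. At stake is how that one display can be read, not the proof-of-concept decision.

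**Working it through.** **Inputs.** Antibody samples at Weeks 2, 4, 8, 12 and 30 (Protocol Table 5-1). Last dose at Week 10 and follow-up visit at Week 30 (Protocol 5.1.2). TEAE window to 140 days after the last dose (SAP 11.2). Half-life basis for the same 140 days in the exposure calculation (SAP 11.1): "5 x 28 days for BKZ and 5 x 20 days for ADA".

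**Reproducing the plan's figure.** 5 × 28 = 140 days, as stated. Last dose at Week 10 is 70 days after the first dose, and 70 + 140 = 210 days. 210 / 7 = 30 weeks, so for a subject who completes dosing the TEAE window closes at the visit of the final antibody sample.

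**Time before the first positive sample.** For first positivity at Week w, the greatest lead of a TEAE over that sample is w weeks, and the share of the nominal window that precedes it is w / 30.

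| First positive | Longest lead | Share of window before the sample | Gap since previous sample |
|---|---|---|---|
| Week 2 | 2 weeks (0.5 month) | 2/30 = 7% | 2 weeks |
| Week 4 | 4 weeks (0.9 month) | 4/30 = 13% | 2 weeks |
| Week 8 | 8 weeks (1.8 months) | 8/30 = 27% | 4 weeks |
| Week 12 | 12 weeks (2.8 months) | 12/30 = 40% | 4 weeks |
| Week 30 | 30 weeks (6.9 months) | 30/30 = 100% | 18 weeks |

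The follow-up visit may fall up to 3 days early (Protocol 8.10), so a subject first positive there has at most about 3 days of the window left.

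**Illustration, on assumptions.** The documents give no distribution for the time of first positivity. Suppose that TEAE onsets are uniform over 30 weeks and that positive subjects have equal event rates and complete follow-up. With a proportion p of positive subjects first positive at Week w, the share of positive-stratum events starting before the first positive sample is the sum of p × w / 30:

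- Spread equally over the five visits: 0.2 × (2 + 4 + 8 + 12 + 30) / 30 = 11.2 / 30 = 37%.
- Mostly early (40, 30, 20, 5, 5%): (0.8 + 1.2 + 1.6 + 0.6 + 1.5) / 30 = 5.7 / 30 = 19%.
- Mostly late (5, 5, 10, 20, 60%): (0.1 + 0.2 + 0.8 + 2.4 + 18) / 30 = 21.5 / 30 = 72%.

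These figures show how far the answer depends on timing. They are not estimates for this trial.

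**The case against.** The strongest reply is that the date of the first positive sample is a poor marker of when antibodies arose, so a label of ever positive is a reasonable choice. There is an 18-week gap between the Week 12 and Week 30 samples. SAP 10 flags samples with bimekizumab above the assay's drug tolerance and excludes them from the antibody summaries, and Protocol 5.4 predicts median troughs above 40 µg/mL on treatment. The tolerance limit is not given, but a subject negative or unevaluable on treatment and positive after washout may have had antibodies earlier. This stands. It means that an event before the first positive sample cannot be said to precede seroconversion, and it is a reason to keep the planned table.

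The reply also bears on the remedy. For a subject first positive at Week 30, the period on or after positivity is almost empty. Time after a positive sample is late study time, while never-positive subjects contribute the whole study. The bimekizumab group has only about 40 subjects. All of this stands as a limit on what the split can show.

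On early leavers, Protocol 8.11 and SAP 4.4 ask them back for Week 12 and for the visit 20 weeks after the last dose, both with antibody samples, and SAP 4.4 assigns early-withdrawal antibody results to the next antibody visit. That reduces the imbalance in sampling but does not remove it.

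Finally, with few subjects the order could be pieced together from the separate listings of visit dates, antibody results and AE onset. That is possible, but no output does it.

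**Conclusion.** The point holds as a gap in a descriptive safety display. TEAEs that started before a subject's first positive sample are counted in the positive stratum, and no planned output shows the order. For one positive subject the affected part of the nominal window runs from 7% (first positive at Week 2) to essentially all of it (Week 30). The total for the trial cannot be stated, because it depends on the timing of first detection.

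A reader might infer more than this, and the documents do not support it:

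- That the SAP attributes events to antibodies. It only counts subjects and events under a subject-level label, and SAP 3.1 confines formal testing to the primary efficacy variable.
- That most events in the positive stratum came months before positivity. That needs late first positivity, which is an assumption; with first positivity at Week 2 or 4 the lead is at most 2 or 4 weeks.
- That any link shown could not be causal. Detection may lag seroconversion.
- That the table was designed to answer a stated objective. The secondary objective names safety and immunogenicity side by side, not a relationship between them.

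Nothing here affects the primary analysis or the success criterion. The change is still worth making, because the data are already held.

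**What to change.** Keep the table by overall status. For the bimekizumab group, add a TEAE table with three columns and the subject-time for each:

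1. Positive subjects, onset before the first positive sample.
2. Positive subjects, onset on or after the first positive sample.
3. Never-positive subjects.

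At minimum, add a flag to the AE listing for onset relative to the first positive sample. Use the actual sample date, since SAP 4.4 moves early-withdrawal antibody results to a later visit label.

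The added output should also:

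- carry a footnote that the first positive sample dates detection and not seroconversion, citing the 18-week gap from Week 12 to Week 30 and the samples above drug tolerance;
- show subjects first positive at Week 30 separately, because they have almost no time on or after positivity;
- state how subjects positive at Baseline are classed.

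The cost is a few lines of SAP text and one table or listing flag. AE onset dates and antibody results by visit are already planned for listing. The downside is small columns that differ in time on study, so the added table must be read as descriptive only.

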11.3 Clinical laboratory evaluations

Laboratory data (chemistry, hematology and urinalysis) and changes from Baseline (if applicable) for numeric variables will be listed by treatment group and visit. Any laboratory variables that are BLQ or ALQ will be handled as described in [Section 4.2.3](#). Values outside the

reference range for the numeric variables will be flagged in the listings and in addition, will be listed separately. The reference ranges will also be reported in the listings.

Chemistry and hematology variables presented in [Table 11–1](#) will be summarized by treatment group at each visit, for both observed values and changes from Baseline. Figures of mean and mean change from Baseline will be presented by treatment for the absolute neutrophil count (ANC). All treatment groups will be overlaid on the same plot and the plot will include the error bars based on the SD (ie, mean +/-SD).

Laboratory variables will be grouped according to the laboratory function panel and categorized as normal, high or low, if applicable, based on the reference range supplied by the analytical laboratory. For selected variables that are identified in [Table 11–1](#), the change in category from Baseline will be presented in shift tables for all post-Baseline visits.

The number and percentage of subjects with treatment-emergent markedly abnormal (TEMA) values will be tabulated by treatment group and visit. Markedly abnormal laboratory values will generally be defined as those categorized as Grade 3 or Grade 4 as per the Rheumatology Common Toxicity Criteria (RCTC) Version 2.0 (Woodworth et al, 2007). Communication with the lead author of the RCTC publication has revealed that the reference ranges for absolute lymphocyte counts (ALC) are in error, therefore ALC criteria will follow the ranges defined as per the Common Terminology Criteria for Adverse Events (CTCAE) Version 4.03 (United States Department of Health and Human Services, 2010). Additional laboratory variables (not present in the RCTC publication) will also be categorized as per the CTCAE Version 4.03. The criteria for identifying TEMA values are presented in [Table 14–7](#) and [Table 14–8](#) for hematology and chemistry values respectively.

Laboratory measurements meeting the criteria for TEMA will be listed separately for hematology and chemistry. The listings will include all measurements for any variable with at least 1 TEMA result for each subject

Table 11–1: Laboratory measurements

Hematology	Chemistry	Urinalysis	Serology
Basophils	Bicarbonate	Albumin	HIV
Eosinophils	Calcium	Bacteria	HLA-B27
Lymphocytes	Chloride	Crystals	Hepatitis B
Atypical lymphocytes	Creatinine	Glucose	Hepatitis C
Monocytes	hsCRP ^a	pH	
Neutrophils ^b	Magnesium	RBC	
Hematocrit	Potassium	WBC	
Hemoglobin ^b	Sodium	Urine dipstick for pregnancy testing ^c	
MCH	Glucose	Urine drug screen	
MCHC	BUN		

Table 11–1: Laboratory measurements

Hematology	Chemistry	Urinalysis	Serology
MCV	ALP ^b		
Platelet count	AST ^b		
RBC count ^b	ALT ^b		
WBC count ^b	GGT ^b		
	Total bilirubin ^d		
	Uric acid		
	LDH		
	Total cholesterol ^b		
	Serum pregnancy testing		
	Serum FSH ^e		

ALP=alkaline phosphatase; ALT=alanine aminotransferase; AST=aspartate aminotransferase; BUN=blood urea nitrogen; FSH=follicle-stimulating hormone; GGT=gamma glutamyltransferase; hsCRP= high sensitivity C-reactive protein; HLA=human leukocyte antigen; HIV=human immunodeficiency virus; LDH=lactate dehydrogenase; MCH=mean corpuscular hemoglobin; MCHC=mean corpuscular hemoglobin concentration; MCV=mean corpuscular volume; RBC=red blood cell; WBC=white blood cell.

^a To avoid duplication, hsCRP will be included in the listings and tabulations for the efficacy data and will not be included in the safety laboratory outputs.

^b Shift tables of the change from Baseline in these variables will be presented.

^c Pregnancy testing will be done in all women of childbearing potential and will consist of serum testing at Screening and at the Safety Follow Up Visit and urine testing at all other visits.

^d If total bilirubin is >ULN (upper limit of normal), a direct bilirubin estimation (%) will be performed.

^e The serum FSH test (at Screening only) should only be performed on postmenopausal females who have been postmenopausal for ≥1 year and last menstrual cycle occurred <2 years ago.

Any additional laboratory variables not included in the outputs described previously will be listed separately. These will include the following:

- Serology
- Urine drug screen
- Pregnancy tests (serum and urine)
- Follicle stimulating hormone (FSH) (only for postmenopausal women)

The results of the TB questionnaire will be listed separately.

Subjects with treatment-emergent liver function test abnormalities at any post-Baseline visit will be summarized (number and percentage of subjects) by treatment group. The criteria for this tabulation are presented in [Table 14–9](#).

